8.2 Secondary Objective(s)

- 1. To evaluate whether the intensity of treatment adherence support affects HCV treatment completion rates.
- 2. To evaluate whether the intensity of treatment adherence support affects HCV treatment adherence.
- 3. To estimate the incidence and correlates of HCV reinfection among HCV mono- and HIV/HCV coinfected PWID who achieve HCV cure.
- 4. To evaluate the impact of HCV cure on HIV viral suppression among HIV/HCV coinfected PWID.

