12.3.2. Documentation of HIV status and antiretroviral therapy regimen

Clients in the ICCs are offered HIV testing every 6 months. These HIV results are maintained in the EHR. In addition, all HIV positive participants who visit a government ART center receive an ART book which maintains a record of all laboratory testing that is done within government ART centers (i.e., CD4 cell count and HIV RNA) and all ART prescriptions and refills including the name of the medications, the number of pills dispensed and the dose. All of this information is abstracted monthly by ICC staff into the EHR. Using this EHR, HIV status, most recent CD4 cell count, HIV RNA level and ART refill will be documented in the screening eCRF. In cases where no HIV test has been done or the most recent HIV antibody test was negative and completed more than three months prior, an HIV antibody test will be required for screening purposes.

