15.3.2. Secondary objectives / hypotheses

15.3.2.1. To evaluate whether the intensity of treatment adherence support affects HCV treatment completion rates.

Hypothesis: Among PWID at elevated risk for treatment failure, PWID receiving the high intensity intervention will have significantly higher treatment completion than those receiving either the medium or the low intensity interventions.

Hypothesis: Among PWID at minimal risk for treatment failure, PWID receiving either the high or the medium intensity intervention will have significantly higher treatment completion than those receiving the low intensity interventions.

15.3.2.2. To evaluate whether the intensity of treatment adherence support affects HCV treatment adherence.

Hypothesis: Among PWID at elevated risk for treatment failure, PWID receiving the high intensity intervention will have significantly higher adherence than those receiving either the medium or the low intensity interventions.

Hypothesis: Among PWID at minimal risk of treatment failure, PWID receiving either the high or the medium intensity intervention will have significantly higher adherence than those receiving the low intensity intervention.

15.3.2.3. To estimate the incidence and correlates of HCV reinfection among HCV mono- and HIV/HCV coinfected PWID who achieve HCV cure.

Hypothesis: HCV reinfection will be lower among clients who have higher attendance at OAT programs.

15.3.2.4. To evaluate the impact of HCV cure on HIV viral suppression among HIV/HCV coinfected PWID.

Hypothesis: Among HIV/HCV co-infected PWID, HIV viral suppression will be higher after achievement of HCV cure.

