Reinfection (secondary outcome). Reinfection will be defined as testing positive for HCV Core Ag after achieving SVR. This may be at any of the post SVR follow-up visits. To evaluate factors independently associated with reinfection, all clients who achieve SVR and have at least one subsequent HCV Core Ag assessment will be included. Using survival analysis, factors associated with reinfection will be assessed. These including ongoing substance use, needle sharing, OAT, SSP use, HIV status and frequency of visits to the ICC. We will also evaluate whether the risk stratum or intervention had impact on reinfection outcomes as well as the reinfection rate over time elapsed since treatment completion. In order to account for missing data due to loss-to-follow-up, we will use inverse-weighting methods.^{97,98}

HIV viral suppression (secondary outcome). Annual assessments of HIV viral load among HIV/HCV coinfected participants in the 7 ICCs are expected as part of other ICC activities and standard of care at Indian government ART centers. All available viral load measurements for HIV/HCV co-infected PWID enrolled in the trial will be used. Viral suppression will be defined as HIV RNA <LLOQ. We will compare viral suppression across two groups defined by primary outcome status, which will be cured vs. not cured using logistic regression with generalized estimating equations (GEE) to account for repeated measures within individuals. All potentially confounding factors known to be associated with HCV cure and HIV viral suppression in this population including demographics, substance use, needle sharing, OAT, SSP use, social support and frequency of visits to the ICC will be accounted for. Analyses will be combined across all groups but we will include a covariate for the classification of risk of treatment failure (minimal or elevated). To evaluate whether the intensity of HCV treatment support also had any impact on HIV viral suppression outcomes, a covariate for the intensity of intervention received will also be included. In order to account for missing data due to loss-to-follow-up, we will use inverseweighting methods. 97,98 Additional sensitivity analyses will vary the threshold for HIV viral suppression to account for blips, considering cutoffs of <200 copies/ml, <500 copies/ml and <1000 copies/ml.

15.7.2.3. Exploratory analysis.

Exploratory outcomes. These are described in the Statistical Analysis Plan.

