Annual assessments of HIV viral load among HIV/HCV coinfected participants in the 7 ICCs are expected as part of other ICC activities and standard of care at Indian government ART centers. All available viral load measurements for HIV/HCV co-infected PWID enrolled in the trial will be used. Viral suppression will be defined as HIV RNA less than LLOQ. We will compare viral suppression across two groups defined by primary outcome status, which will be cured vs. not cured using logistic regression with generalized estimating equations (GEE) to account for repeated measures within individuals. Because these groups will be defined by the primary outcome and no longer balanced by randomization, analysis will be adjusted for confounding factors including demographics, substance use, needle sharing, MOUD, SSP use, social support and frequency of visits to the ICC. Analyses will be combined across all groups but we will include a covariate for the classification of risk of treatment failure (minimal or elevated) and intervention received. In order to account for missing data due to loss-to-follow-up, we will use inverse-weighting methods.^{4,5}

2d.1. Sensitivity analyses. We will vary the threshold for HIV viral suppression (<150 copies/ml vs. 400 copies/ml vs. 1000 copies/ml) and will also incorporate the revised definition of SVR vs. treatment failure using sequence data.

3. Exploratory analysis

3a. Impact of interventions on medication for opioid use disorder (MOUD) utilization. Daily MOUD utilization data is available in the electronic health record. We will explore the impact of the interventions within strata by arm on new MOUD initiation and MOUD retention using methods of survival analysis, logistic regression with GEE and growth mixture models. Analyses will be adjusted for site. Additional sensitivity analyses will be similar to those reported in the primary and secondary outcome analyses and will include accounting for the prognostic score.

3b. Impact of interventions on quality of life.

Quality of life data is captured at the SVR visit and at semi-annual post-treatment follow-up visits. Using logistic and linear regression with GEE, we will explore the impact of interventions within strata on quality of life after treatment.

3c. Impact of interventions on mortality.

Using Poisson regression, we will explore the impact of interventions within strata on all-cause mortality.

3d. Effect of delays in treatment completion on SVR.

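### The HIV suppression analysis (SAP 2d) compares cured with not cured participants without a pre/post term and without naming entry HIV suppression or ART, so a difference that predates cure can be read as an effect of cure.

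*SAP*

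**What the plan says.** Protocol 8.2 sets the objective: "To evaluate the impact of HCV cure on HIV viral suppression among HIV/HCV coinfected PWID". Protocol 15.3.2.4 states the hypothesis: "Among HIV/HCV co-infected PWID, HIV viral suppression will be higher after achievement of HCV cure". The objective is causal and the hypothesis is about before and after.

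SAP 2d sets the data and the contrast: "All available viral load measurements for HIV/HCV co-infected PWID enrolled in the trial will be used", and "We will compare viral suppression across two groups defined by primary outcome status, which will be cured vs. not cured using logistic regression", with GEE for repeated values. It recognises that randomisation no longer protects the comparison ("Because these groups will be defined by the primary outcome and no longer balanced by randomization") and responds with covariates: "analysis will be adjusted for confounding factors including demographics, substance use, needle sharing, MOUD, SSP use, social support and frequency of visits to the ICC". It adds the risk class, the intervention received and inverse weighting for loss to follow-up. The sensitivity analyses in SAP 2d.1 change only the suppression threshold and the SVR definition.

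Protocol 15.7.2.2 plans the same contrast and promises more on confounding: "All potentially confounding factors known to be associated with HCV cure and HIV viral suppression in this population including demographics". The list that follows likewise omits ART and suppression at entry.

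The data exist. Protocol 12.3.2 says: "HIV status, most recent CD4 cell count, HIV RNA level and ART refill will be documented in the screening eCRF". Protocol 12.3.7 takes a full ART history, and 12.2.4 and 12.2.5 abstract HIV RNA again at the SVR and post-SVR visits.

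**The concern.** Cure depends on taking DAAs, and HIV suppression depends on taking ART. If the same people do both reliably, the cured group was already more often suppressed at entry. A cured versus not cured contrast with no entry value and no period term cannot separate that standing difference from a change after cure.

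The trial itself makes such a link plausible. Protocol 15.5 uses early ART refills and HIV suppression as the surrogate for HCV treatment failure. If cure status follows the primary outcome definition, the not cured group also contains participants who died or were lost to follow-up, which can widen a difference in engagement.

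At stake is secondary objective 4: an adherence difference could be reported as a benefit of HCV cure for HIV control.

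**Working it through.** The documents give no suppression rate, number of co-infected participants or power for this endpoint, so there is no planned figure to reproduce. All rates below are assumptions, and the true effect of cure is zero throughout.

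**Step 1, by hand.** Suppose suppression is 70% in the cured and 60% in the not cured, at entry and afterwards alike. The cured versus not cured odds ratio (OR) is (0.70/0.30)/(0.60/0.40) = 2.33/1.50 = 1.56. For 65% versus 60% it is (0.65/0.35)/(0.60/0.40) = 1.86/1.50 = 1.24. In both cases the after-OR divided by the before-OR is 1.00: nothing changed with cure.

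**Step 2, simulation with partial adjustment.**
- Latent adherence A and a person effect u are standard normal.
- Logit of suppression: 0.5 + gA + u at entry and 0.8 + gA + u at three post-SVR values.
- Logit of ART at entry: 1.4 + gA. Logit of SVR: 2.2 + dA (SVR 87–90%).
- (d, g) = (0, 0.8) no link, (0.4, 0.8) moderate, (1.0, 1.5) strong.
- The risk score and ICC visits each correlate 0.5 with A. Arms are allocated 3:2:1 or 1:2:3 by risk class, as in Protocol 15.5.
- SVR is missing in 15%, at random or linked to A, and counted as failure or excluded.
- Each behavioural covariate, standing in for items such as substance use or social support, correlates 0.5 with A.

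The first three rows pool entry and post-SVR values, as a literal reading of SAP 2d allows. Ranges run over the missing-SVR variants; the four-covariate row covers missing counted as failure only.

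| Model | Moderate | Strong |
|---|---|---|
| Risk class, arm, ICC visits | 1.07–1.19 | 1.38–1.95 |
| … plus one behavioural covariate | 1.06–1.16 | 1.31–1.77 |
| … plus four behavioural covariates | 1.04–1.10 | 1.21–1.51 |
| Post-SVR values; row 1 plus entry suppression and ART | 1.05–1.14 | 1.24–1.55 |
| … with 30% of entry HIV RNA missing at random | 1.06–1.15 | 1.26–1.62 |
| … complete entry data, plus one behavioural covariate | 1.04–1.12 | 1.21–1.48 |

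With no link, the row 1 model gives 1.00–1.01.

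**Step 3, what entry adjustment gains.** Compare row 4 with row 1, missing SVR linked to adherence and counted as failure. The share of the log-OR removed is 1 − ln(1.14)/ln(1.19) = 1 − 0.131/0.174 = 25% (moderate) and 1 − ln(1.55)/ln(1.95) = 1 − 0.438/0.668 = 34% (strong). If the entry value tracks adherence only half as well, the gain almost vanishes: 1.16–1.17 before and after (moderate), 1.72–1.83 against 1.72–1.82 (strong).

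**Step 4, the period-by-cure interaction.** It is 0.99–1.01 (up to 1.04 in repeat runs) when adherence acts equally on entry and later values. With the half-strength entry value it is about 1.1 (moderate) and 1.5 (strong).

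**Step 5, the window.** Post-SVR values alone give the same OR as pooled values (1.95 in both for the strong, linked, failure case). The choice of window does not itself create the bias.

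**The case against.** The best defence is that the plan already covers this in principle. The SAP says the groups are unbalanced, both lists are open-ended, and the Protocol promises to account for all known confounders. The risk class comes from a score built on ART behaviour, and ICC visits and substance use also carry information on adherence. This stands in part. Nothing bars adjustment for ART or entry suppression; the gap is that the most direct measures are not pre-specified and the named ones give only partial control. The risk class is a two-level prediction, not the participant's own entry status.

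A second point concerns size. A model with only risk class, arm and ICC visits is thinner than SAP 2d, so its 1.38–1.95 in the strong case overstates the problem. The same applies to a simulation adjusted for risk stratum alone, in which 34% to 99% of runs were falsely significant when a link existed (300 or 600 co-infected participants assumed). A reader might infer that the planned test has such error rates. The documents do not support that, because the fuller covariate list lowers the bias.

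Third, Protocol 8, 9, 12.2.5 and 15.1 treat suppression as an outcome after treatment. If only later values enter, the main model has no pre-period, and a period term belongs in a sensitivity analysis. A reader might also infer that using all viral loads is itself the source of bias; step 5 shows otherwise.

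Finally, entry adjustment is only a partial remedy. That is correct, and it bears on how the result should be reported.

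**Conclusion.** The concern holds as one of residual confounding by prior ART adherence in a non-randomised secondary comparison. A hypothesis about change after cure is tested by a between-person contrast that omits the two most relevant entry measures, both already collected, and no planned sensitivity analysis would reveal a difference present before cure.

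On assumed inputs with several behavioural covariates adjusted, the spurious OR is about 1.04–1.10 for a moderate link and 1.2–1.5 for a strong one. It is larger with fewer covariates and 1.0 with no link. These figures rest on the assumed strength of the ART–DAA adherence link and on covariates that each correlate 0.5 with adherence. Inverse weighting was not simulated. The documents do not establish that the link exists in this cohort, only that the trial relies on something like it for its risk score.

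A reader might infer that the plan forbids or ignores adjustment, or that the SVR comparison by arm is affected. Neither follows: the covariate lists are open, and the primary analysis compares randomised arms. Only secondary objective 4 is affected.

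**What to change.** In SAP 2d and Protocol 15.7.2.2:

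1. Name entry HIV RNA suppression and ART status/refill as covariates. Record the date of the entry HIV RNA, and handle missing entry values by multiple imputation.
2. Pre-specify the pre/post by cured interaction as a sensitivity analysis.
3. State that the main contrast uses post-treatment values, counted from the same origin for everyone: the scheduled SVR week, 24 or 36 by treatment duration. The actual visit date for attendees (10–60 weeks after treatment) with a scheduled week for non-attendees would make the origin differ by exposure group, because non-attendees are all not cured if missing SVR counts as failure. Protocol 15.6 already follows co-infected participants whatever their SVR result.
4. Report the result as an association.

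The cost is wording plus abstraction of one date. There are limits. Protocol 12.3.2 sets no age limit on the entry HIV RNA, 12.3.9.9 abstracts only available results, and viral loads are expected about yearly. With an old or absent value, adjustment gains little and the interaction is not fully unbiased. The 30% missing case above used a missing-value category under random missingness; imputation was not simulated. On the assumed inputs (600 co-infected participants), the standard error is about 1.07–1.09 times the planned one for the adjusted model and 1.4–1.6 times for the interaction.

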Arm 3: High intensity intervention: The high intensity intervention will involve patient-centered DOT with flexibility in terms of the frequency of pickup and the site of DOT (ICC, field-based) with a minimum of at least 1 observed dose per week. Participants in this arm will also receive PN support for overcoming barriers and service linkage similar to participants in Arm 2. The main differences between Arms 2 and 3 are: (i) medications will not be dispensed for more than one week at a time (to coincide with OAT dosing, where applicable); and (ii) ≥1 dose/week will be observed.

To measure adherence, brief surveys and pill counts will be conducted at each medication pick up/ drop off. In the high intensity intervention, a computerized system will track client doses that are observed using biometrics, including doses delivered in the field.

Persons will be treated for HCV according to the standard of care in India. Minimal laboratory monitoring will be used except when clinically indicated. Clients with decompensated cirrhosis will be excluded from treatment.

All HIV/HCV co-infected participants and those HCV mono-infected participants who achieve SVR will be followed post SVR assessment. These individuals will be followed every six months after the SVR assessment to assess HCV reinfection and HIV viral suppression (among HIV/HCV coinfected participants) for up to 48 months after SVR. In each ICC, an electronic health record (EHR) is already in place. This system captures information on general patient characteristics,

medical history including diagnoses, laboratory testing, and treatment received including systematic assessment of ART refills. The system is designed to capture information on care delivered in the ICC (e.g., OAT, SSP) and other government centers (e.g., TB treatment). All treatment dispensation, adherence, and treatment outcomes including HCV RNA testing will be captured in this database. Re-infection will be assessed using the Abbott ARCHITECT HCV Ag assay which is highly sensitive (97-100%) in identifying HCV RNA^{88,89} and in a small study of re-infection demonstrated 100% sensitivity/specificity of identifying recurrence of virus post-SVR.⁹⁰

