12.2.2. Entry/Enrollment evaluations

Entry evaluation for most will take place on the same day as the screening. If not, the maximum time allowable is 90 days from when the laboratory testing for HCV treatment eligibility has been completed. For participants who do not want to complete entry evaluations on the same day as screening, appointments will be scheduled as soon as possible (i.e., 1-2 days).

At the Entry Visit, the Study Nurse should first administer the **Entry Visit Behavioral Survey** to inform randomization. The Entry Visit survey includes the following modules. The survey will be completed in an eCRF.

- Demographics
- Social / family support
- Quality of life
- Substance use, risk behavior and treatment

In addition, at the Entry visit, participants will undergo a laboratory draw for specimen repository storage and women of childbearing potential will have a pregnancy test.

While COVID-19 safety precautions are in place, the Entry Visit Behavioral Survey will be completed over the phone rather than face-to-face in order to reduce the risk to study staff and participants.

The following additional activities will take place at the entry visit after completion of the survey.

- Randomization (See Section 15.5 for details): The propensity for treatment non-adherence will be determined by an algorithm (not shared with participants or site staff) and accordingly participants will be randomized to receive low, medium or high intensity treatment support. The Study Nurse will use the randomization tab in the EHR to assign the participant to the corresponding Study Arm (level of treatment support).
- Update contact/locator information

Additional activities at the Entry Visit will differ by study Arm

• Preparation for HCV treatment adherence support

June 30, 2022

- Arm 1 Meet with a PN to receive standard adherence counseling
- Arm 2- Assignment to a PN
 PN to complete **Patient Navigation Form** to identify barriers and services needed
 - PN to complete **Hepatitis C Care Plan** including information on schedule/frequency of contact and referrals
 - PN to prepare Contact Log
- Arm 3 Assignment to a PN
 - Jointly meet with PN/Nurse to complete Patient Navigation Form
 - PN to complete Hepatitis C Care Plan
 - PN to schedule frequency/location of DOT visits
 - PN to begin **DOT Log**
- Observation of first dose (All Arms)
- Schedule next appointment/contact
 - o Arm 1: 4 weeks
 - o Arm 2: 4 weeks

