12.3.10. Questionnaires

Screening questionnaire. This will be a brief questionnaire to capture other screening criteria including intention to migrate, psychological fitness, pregnancy intentions, etc.

Responses should be recorded in a screening eCRF. This is a one-time questionnaire.

Demographics questionnaire

This questionnaire will be adapted from questionnaires previously used in this population to capture age, sex, marital status, education, income and housing status.

Responses should be recorded in an eCRF. This questionnaire will be administered at the Entry visit, SVR evaluation visit, and post-SVR visits.

Social/family support

We will use the Medical Outcomes Study Social Support Survey⁹³ which captures information on functional support in five dimensions (emotional, informational, tangible, positive social interaction and affectionate). Additional questions will be asked about disclosure of HCV/HIV and substance use to family members/friends.

Responses should be recorded in an eCRF. This is a one-time questionnaire that will be administered at the Entry visit.

Quality of life

The EQ-5D is a validated instrument used to collect data about quality of life (http://www.euroqol.org). The instrument asks questions and each has three possible responses (EQ5D-3L version). The instrument asks respondents to comment on their degree of mobility, self-care, usual activities, pain/discomfort, and anxiety/depression, and then ask participants to record their current health-related quality of life state using a vertical visual analogue scale (0-100 range). The instrument has been translated into a variety of languages including Hindi and Punjabi and is available as a paper form, a computer-based form, a tablet/cell phone form, or as an interview.

Responses should be recorded in an eCRF. This questionnaire will be administered at the Entry visit, SVR evaluation visit, and post-SVR visits.

Substance Use and Risk Behavior Questionnaire

We will use a questionnaire that has been adapted from a variety of sources (WHO ASSIST,⁹⁴ PhenX toolkit, AUDIT and existing survey) for use in India. This survey includes information on the type, route and frequency of drug and alcohol use. In addition, this survey will collect information on risk factors for nonadherence and for reinfection including data on the types and numbers of sharing/network partners, locations of drug injection, use of shooting galleries and incarceration.

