15.3 Study Objectives and Hypothesis/Hypotheses

15.3.1. Primary objective / hypotheses

Primary objective: To evaluate whether the intensity of treatment adherence support affects sustained virologic response rates in HCV mono- and HIV/HCV co-infected participants receiving DAAs in PWID-focused centers

Hypotheses:

- Among PWID at elevated risk for treatment failure, PWID receiving the high intensity intervention will have significantly higher SVR than those receiving either the medium or the low intensity interventions.
 - 1a. Among PWID at minimal risk for treatment failure, PWID receiving either the high or the medium intensity intervention will have significantly higher SVR than those receiving the low intensity interventions.

The formal null hypothesis is no difference in SVR and the alternate is a difference in SVR. The trial is designed for superiority assessment; however, if there is failure to detect a statistically significant difference between support strategies across any particular stratum, a lesser objective of interest is non-inferiority with a pre-specified non-inferiority margin.

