15.6 Participant Enrollment and Follow-up

We anticipate enrolling 3,000 (approximately 420 per site) persons over a period of 18-24 months with an average of 15-20 participants per site per month. After enrollment, participants will be followed while they are on treatment (for 12 or 24 weeks) through to an SVR evaluation visit 10 – 60 weeks after treatment completion. This will be the minimum amount of follow-up for all those enrolled. Following this, those who achieve SVR and those who are HIV/HCV co-infected (regardless of SVR) will have semi-annual visits thereafter to monitor reinfection. Follow-up will be complete at the SVR evaluation visit for those who do not achieve SVR and are not HIV/HCV coinfected. The maximum follow-up post the SVR evaluation visit for those who achieve SVR is 30 months for a total follow-up of 36 months. The goal will be that everyone who achieves SVR has at least one semi-annual visit after the SVR evaluation visit but it is possible that some individuals who are enrolled late do not have any post SVR follow-up.

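### SAP 3b leaves out the Entry EQ-5D, and its arm comparison draws on post-SVR visits held only for cured or HIV/HCV co-infected participants

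*SAP*

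**What the plan says.** SAP 3b consists of two sentences. The first lists the time points: "Quality of life data is captured at the SVR visit and at semi-annual post-treatment follow-up visits". The second gives the model: "Using logistic and linear regression with GEE, we will explore the impact of interventions within strata on quality of life after treatment". Neither mentions a baseline value, site, visit-specific contrasts, weighting, or a rule for missing data and deaths.

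The protocol collects more than SAP 3b lists. On the EQ-5D, Protocol 12.3.10 says: "This questionnaire will be administered at the Entry visit, SVR evaluation visit, and post-SVR visits". Table 12.1 marks the same questionnaire at Entry. Protocol 12.2.2 places the survey containing the quality-of-life module ahead of randomization: "At the Entry Visit, the Study Nurse should first administer the" behavioral survey, with the arm assigned afterwards.

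The protocol also limits who has later visits. Section 9 states: "All HIV/HCV co-infected participants and those HCV mono-infected participants who achieve SVR will be followed post SVR assessment". Section 15.6 gives the other side: "Follow-up will be complete at the SVR evaluation visit for those who do not achieve SVR and are not HIV/HCV coinfected".

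**The concern.** There are two separate issues.

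The first is precision. A pre-randomization EQ-5D exists for the same people on the same scale, and the plan does not use it. SAP 3a, directly above, adjusts for site; 3b does not say so.

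The second is selection. The trial expects arm to change SVR. In the elevated-risk stratum the hypothesis is that "PWID receiving the high intensity intervention will have significantly higher SVR than those receiving either the medium or the low intensity interventions". If so, arm also changes who has post-SVR visits. An arm that cures fewer people keeps a more selected group at the later visits. If people with better underlying quality of life are also more likely to be cured, that arm's later scores look better than they should. The contrast then tilts against the arm that cures more. Where all retained participants are cured, any quality-of-life benefit that works through cure also drops out of the comparison.

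The SAP deals with related problems elsewhere. Section 2d acknowledges that groups defined by cure are no longer balanced by randomization, and 2c and 2d use inverse weighting for loss to follow-up. Section 3b does neither.

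**Working it through.** The documents give no SD, effect size, correlation or power for quality of life, so there is no plan figure on this point to reproduce. As a check on the arm sizes only, Table 15.4.1 was re-solved for the elevated stratum at N=1500 (two-sided 0.05, 80% power, comparator SVR 0.85). The detectable RR is 1.075 for high vs low (stated 1.08) and 1.062 for high vs medium (stated 1.06), so the table reproduces.

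1. **Precision, linear model, one post-treatment value.** Adjusting for baseline multiplies the variance by 1 − r². The correlation r is assumed.
   - r = 0.4: 1 − 0.16 = 0.84, a 16% reduction.
   - r = 0.6: 1 − 0.36 = 0.64, a 36% reduction.
   - Detectable difference in SD units = (1.960 + 0.842) × √(1/n₁ + 1/n₂) × √(1 − r²).
   - 750 vs 250: 2.802 × 0.0730 = 0.205 unadjusted; 0.188 at r = 0.4; 0.164 at r = 0.6.
   - 750 vs 500: 2.802 × 0.0577 = 0.162 unadjusted; 0.148 at r = 0.4; 0.129 at r = 0.6.

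2. **Who is eligible for post-SVR visits.** Share = SVR + (1 − SVR) × h, where h is the HIV share (assumed 0 to 30%).
   - Lowest: 0.80 + 0.20 × 0 = 80%.
   - Highest: 0.95 + 0.05 × 0.30 = 96.5%.
   - So 3.5% to 20% are excluded, all of them failures. This is an upper bound on what the rule removes, because the intention-to-treat SVR counts deaths and losses as failures, and those people may lack an SVR-visit EQ-5D as well.

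3. **Size of the distortion.** This was simulated with 2 million participants per arm.
   - SVR pairs come from Table 15.4.1: 0.80 × 1.09 = 0.872 and 0.85 × 1.08 = 0.918.
   - Assumptions: a lasting quality-of-life component carries half the variance and correlates c = 0.3 or 0.5 with the propensity for cure; h = 0 or 20%; everyone is seen at the SVR visit; arm acts on quality of life only through SVR.
   - Five post-SVR visits follow from Protocol 15.6: "The maximum follow-up post the SVR evaluation visit for those who achieve SVR is 30 months", and 30/6 = 5. Section 9 and Table 12.1 allow 48 months and eight visits, which would move the pooled figures towards the post-SVR-only ones.

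| Contrast, high minus low (SD) | No true effect | Cure adds 0.3 SD |
|---|---|---|
| SVR visit, everyone | about 0 | +0.020 to +0.022 |
| Post-SVR visits only | −0.017 to −0.039 | −0.012 to −0.039 |
| SVR plus five later visits, pooled | −0.013 to −0.031 | −0.004 to −0.027 |

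The true difference in the last column is 0.3 × 0.072 = 0.0216 or 0.3 × 0.068 = 0.0204, which the SVR-visit contrast recovers. The pooled contrast reverses its sign in every scenario run.

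4. **Can weighting repair it?** Inverse weights need a positive chance of being observed. A mono-infected participant without SVR has no scheduled visit after the SVR evaluation, so that chance is zero by design and no weight exists.

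**The case against.** The strongest reply is about scope. Section 3b is exploratory, and quality of life appears in no objective, endpoint or hypothesis. No primary or secondary conclusion depends on it. That stands, and it limits the point to a minor improvement.

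A second reply is that two sentences do not exclude baseline adjustment, and that GEE with visit terms can give visit-specific contrasts. That also stands: the fair statement is that 3b does not specify these things, leaving the choice open until the data are seen. Visit-specific contrasts would still be selected at every post-SVR visit.

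Third, the distortion is small. The largest pooled shift, 0.031 SD, is about one fifth of the smaller unadjusted detectable difference (0.031/0.162 = 0.19). The sign reversal needs an assumed cure benefit and concerns a true difference of about 0.02 SD, which this trial could not detect. Selection is partial too, because co-infected failures stay in follow-up.

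Three stronger readings are tempting but not supported:

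- A reader might infer that the same follow-up rule biases the mortality analysis in SAP 3c. Section 3c states no period, population or person-time, and Protocol 10.3 records deaths where available and keeps tracking people who miss post-treatment visits until death or migration is documented. Whether this covers those whose follow-up ended at the SVR visit is unclear, so an effect is possible but not shown.
- A reader might take the whole failure share, say 8% vs 15% at SVR of 92% vs 85%, as the loss caused by the rule in each arm. It is only an upper bound, for the reason in step 2.
- A reader might infer that leaving out the baseline biases the result. Within a randomized stratum it costs precision only.

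**Conclusion.** The point holds as a low-severity gap in an exploratory analysis. SAP 3b does not use an EQ-5D measurement that the protocol collects before randomization, states no site term, and includes visits whose existence depends partly on the primary outcome.

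The selection follows from the protocol's own follow-up rule and needs no assumption. Its effect on the contrast does: about 0.01 to 0.03 SD against the arm that cures more, under assumed links between quality of life and cure and an assumed HIV share. The precision gain of 16% to 36% rests on an assumed correlation and a single linear outcome. It does not carry over to the logistic model, where adjustment also changes the odds ratio being estimated.

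**What to change.** Rewrite SAP 3b along these lines:

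- The randomized contrast is the SVR-visit EQ-5D by arm within risk stratum, adjusted for Entry EQ-5D and site.
- State a method for missed SVR visits, for example multiple imputation using Entry EQ-5D, arm and site. State separately how deaths are handled. Visits missed in prison (Protocol 18.2.2) fall under the same rule.
- If a dichotomized version is kept, say whether the adjusted odds ratio or a standardized effect is reported. The SAP already uses a standardized estimator for SVR.
- Report post-SVR visits separately, labelled as conditional on cure or HIV status. Do not rely on inverse weighting to restore the mono-infected failures.

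This changes SAP wording only; the data are already being collected. There is a small real cost: longer-term quality of life is no longer presented as a randomized comparison. The SVR-visit analysis will also still depend on the missing-data method chosen.
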